ROSA Total Knee Post Market Study

A prospective, multicenter, EMEA post market clinical follow up
of the ROSA® Knee System

CME2019-24K

V3.0, 4 February 2020

STUDY SPONSOR

Zimmer GmbH Clinical Affairs

[name]

[name]

Switzerland

Study Synopsis

Title	ROSA Total Knee Post Market Study – a prospective, multi-center EMEA post market clinical follow up study for the ROSA Total knee system
Protocol Number	CME2019-24K
Sponsor	Zimmer GmbH
Manufacturer	Zimmer CAS, [name]
Study Device(s)	ROSA® Knee System
Study Objectives/Endpoints	
The main purpose of this study is to collect and compare clinical outcomes data using the commercially available ROSA Total Knee Robotic instrumentation and conventional instrumentation.
 
This will be achieved by assessing:
 
 1. Planned vs actual component positioning 2. Operative workflow efficiency 3. Patient safety based on incidence and frequency of adverse events 4. Clinical performance measured by overall pain and function, health- related quality of life data, and radiographic parameters. 
Primary endpoint: Evaluate the accuracy of implant alignment for ROSA total knee robotic instrumentation compared to conventional instrumentation, by measuring femoral rotation in the axial plane using pre op and post op CT assessments.
 
Secondary endpoints: Measure operative workflow efficiency by recording following time points during surgery: Patient in –and out time, incision – and incision closed time
 
Evaluate the change of the following scores between baseline and each post-operative follow up for performance and clinical benefits:
 
 • Oxford Knee Score • Objective Knee Assessment • Patient Satisfaction • EQ-5D • NRS Pain • FJS-12
Indications/Target population	Patients qualifying for primary total knee arthroplasty who meet the inclusion/exclusion criteria for study participation

Inclusion/Exclusion criteria	
Inclusion criteria:
 
 • Patient is a minimum of 18 years of age • Independent of study participation, patient is a candidate for commercially available Persona, NexGen, or Vanguard knee components implanted in accordance with product labeling • Patient has participated in this study-related Informed Consent Process • Patient is willing and able to provide written Informed Consent by signing and dating the EC approved Informed Consent form • Patient is willing and able to complete scheduled study procedures and follow-up evaluations 
Exclusion criteria:
 
 • Patient is currently participating in any other surgical intervention studies or pain management studies • Patient has undergone contralateral UKA or TKA within the last 18 months • Hip pathology with significant bone loss (e.g. avascular necrosis of the femoral head with collapse, severe dysplasia of the femoral head or the acetabulum) • Hip pathology severely limiting range of motion (e.g. arthrodesis, severe contractures, chronic severe dislocation) • Patient is pregnant or considered a member of a protected population (e.g., prisoner, mentally incompetent, etc.) • Patient has previously received partial or total knee arthroplasty for the ipsilateral knee
Study Design	
Prospective, multicenter study, using Zimmer Biomet commercially available Persona, NexGen and Vanguard total knee implant system. Each consecutive, potential and eligible patient presenting as a candidate for primary knee arthroplasty will be offered study participation.
 
Selection process should be rotated on an equal basis. (eg. 5 Robotic TKA's followed by 5 Conventional TKA's and so on until enrolment is complete)

Clinical Phase	Post market
Sample Size	Maximum 8 EMEA sites, with participating surgeons contributing from 20 of each robotic and conventional knees per site. Maximum study enrolment of 240 subjects in total, including 40 subjects in the CT sub cohort
Length of Study	2,5 years (1,5 year enrolment with 1 year of follow-up). Follow-up visits at 6 weeks, 3 months and 1 year.

Materials and Methods	
Inclusion of 240 eligible subjects within maximum of 8 EMEA sites, divided into 2 groups (robotic and conventional group).
 
Sub cohort of 40 subject for CT assessment and analysis
 
Prospective follow up visit until 1 year post-operative with clinical and radiographic assessments.

Data Collection	
Web based database (Electronic data capture system)

Statistical Reporting	
Performance will be evaluated for pain, function, health- related quality of life, and planned component position vs post-op component position. Data will be summarized descriptively additional to evaluation of data on surgical technique and instrumentation. Categorical data (e.g., gender or race) will be summarized using counts and percentages with 95% Confidence Interval (CI) limit over the time period of interest. Continuous data, such as age, will be summarized by using means, medians, SD, minimum, maximum, and 95% CI over the time period of interest. Implant survival and return to function will be summarized using a Kaplan-Meier method and presented with rates (as percentages) and CI.
 
Routine summaries of complication data is represented by frequencies and percentages. The sample size is based on a longitudinal data collection model and using functional outcomes as secondary endpoints.
 
The data from the CT sub cohort will detect for a difference in deviation from the initial alignment target proportions and presented with rates (as percentages) and CI.
 
Continuous data from pre and post-operative CT measurement will be summarized by using means, medians, SD, minimum, maximum and 95% CI over the time period of interest.

Scores/Performance Assessments	
Clinical performances are assessed by the following scores:
 
 • Oxford Knee Score • Objective Knee Assessment • Patient Satisfaction • EQ-5D • NRS Pain • FJS-12 
Radiographic performances are assessed by:
 
 • Radiographic imaging method pre- and post-operatively • Sub cohort for CT scan pre- and post-operatively
Standards	
The PMCF is compliant with the below:
 
 • The Declaration of Helsinki (DoH) - Ethical principles for medical research involving human subjects. [1] • ISO 14155: 2011 - Clinical investigation of medical devices for human subjects - Good clinical practice. [2]

References

- [1] WORLD MEDICAL ASSOCIATION DECLARATION OF HELSINKI, Ethical Principles for Medical Research Involving Human Subjects, Version October 2013.
- [2] ISO 14155:2011 International Standard for Clinical investigation of medical devices for human subjects -- Good clinical practice.

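### The stated purpose is to compare robotic with conventional instrumentation, but no between-arm estimate is defined for the secondary scores or theatre times

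*Combined protocol and SAP*

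**What the plan says.** All references are to the Study Synopsis in the combined protocol and SAP.

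- **Study Objectives/Endpoints, purpose:** "The main purpose of this study is to collect and compare clinical outcomes data", under robotic and conventional instrumentation. The aims listed beneath it include workflow efficiency and clinical performance, so the comparison is not confined to alignment.
- **Study Objectives/Endpoints, secondary scores:** "Evaluate the change of the following scores between baseline and each post-operative follow up for performance and clinical benefits". Six instruments are listed.
- **Study Objectives/Endpoints, workflow:** "Measure operative workflow efficiency by recording following time points during surgery". The points are patient in, patient out, incision, and incision closed.
- **Study Design:** "Selection process should be rotated on an equal basis", with alternating runs of five as the example. No randomisation is described.
- **Sample Size:** "Maximum study enrolment of 240 subjects in total, including 40 subjects in the CT sub cohort". The Materials and Methods row splits these subjects into a robotic and a conventional group.
- **Length of Study:** "Follow-up visits at 6 weeks, 3 months and 1 year". None is named as the main visit.
- **Statistical Reporting:** continuous data receive the usual summary statistics with a 95% CI, and categorical data receive counts and percentages with a 95% CI. Return to function is to be summarised by Kaplan-Meier with CIs. Data on surgical technique and instrumentation are also to be evaluated, but no quantity is named. Wording about detecting a difference appears only for the CT sub cohort.

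**The concern.** A study whose purpose is to compare two techniques needs, for each outcome, a quantity that expresses the comparison. For the scores and theatre times the plan supplies summaries that could be tabulated for each arm, or for everyone together, without the comparison ever being made. A mean improvement of a given size after knee replacement is compatible with robotic instrumentation being better, worse or the same.

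There are two consequences. First, the secondary part of the stated purpose has no defined answer. Second, if the comparison is made later, the form of the estimate (follow-up score, change score, or baseline-adjusted) and the visit to emphasise can be chosen after the results are known. Allocation is by rotation, so some baseline difference between arms is possible, and in that case the choice of estimate alters the result.

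**Working it through.** **1. What is defined, endpoint by endpoint**

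| Endpoint | Quantity defined | Between-arm quantity? |
|---|---|---|
| Femoral rotation on CT (primary) | Alignment accuracy, robotic compared with conventional | Yes, in words |
| Six clinical scores | Change from baseline to each follow-up | None |
| Theatre times | Four recorded time points | None |
| Return to function | Kaplan-Meier rates with CI | Not stated to be by arm, nor tied to the listed scores |

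The planned 95% CI belongs to a summary statistic. Nothing says that it is by arm, and nothing says that it is for a difference.

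**2. The plan's own figure**

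The maximum of 240 cannot be reproduced, because no significance level, power, effect size, SD or dropout is given. Equal rotation implies 240 / 2 = 120 per arm, which is used below as a best case.

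**3. Precision of the missing estimate**

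Assumptions, none of them in the documents: 120 complete subjects per arm; the score has the same SD (set to 1) in both arms and at both times; the correlation ρ between baseline and follow-up is 0.3, 0.5 or 0.7.

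Common factor: t(238) × √(2/120) = 1.970 × 0.1291 = 0.254. This is also the half-width, in SD units, for an outcome without a baseline, such as a theatre duration.

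- Unadjusted change-score difference: half-width = 0.254 × √(2(1 − ρ))
- Baseline-adjusted difference: half-width = 0.254 × √(1 − ρ²)

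| ρ | √(2(1 − ρ)) | Change score | √(1 − ρ²) | Adjusted |
|---|---|---|---|---|
| 0.3 | 1.183 | 0.301 | 0.954 | 0.243 |
| 0.5 | 1.000 | 0.254 | 0.866 | 0.220 |
| 0.7 | 0.775 | 0.197 | 0.714 | 0.182 |

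The ratio of adjusted to change-score width is √((1 + ρ)/2) = 0.81, 0.87 and 0.92. The adjusted interval is therefore narrower by about 19%, 13% and 8%.

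With 100 complete subjects per arm the common factor is 0.279. The adjusted half-widths become 0.266, 0.242 and 0.199 SD.

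**4. How far the two estimates can part**

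Let the arms differ by b at baseline and by f at follow-up. The change-score difference is f − b and the adjusted difference is f − ρb, so the gap is (1 − ρ)b. For an assumed b of 0.2 SD the gap is 0.7 × 0.2 = 0.14, 0.5 × 0.2 = 0.10 and 0.3 × 0.2 = 0.06 SD. At low correlation that is more than half of the adjusted half-width (0.14 / 0.243 = 0.58), so the choice matters.

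**The case against.** The strongest reply is that this is a post-market follow-up with descriptive reporting, known here only through its synopsis, and that the primary endpoint is plainly comparative. The plan to evaluate data on technique and instrumentation may be meant to cover the rest. If the summaries are split by arm, their means and SDs, together with group sizes, let any reader work out an unadjusted difference and its CI.

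Much of this stands. It would be wrong to infer that the study makes no comparison, and fuller text may exist elsewhere. But the synopsis does not say that the summaries are split by arm, and the phrase on technique and instrumentation names no quantity. A difference with its CI is itself descriptive and requires no hypothesis test.

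Three stronger readings are tempting, and the documents do not support them.

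- **That the plan loses power by judging overlap of per-arm CIs.** At 120 per arm, two per-arm intervals separate only from 2 × 1.980/√120 = 0.36 SD, whereas the interval for the difference excludes zero from 0.25 SD. That is an illustration only, because no such reading rule is planned.
- **That function has no analysis over time.** The Kaplan-Meier summary of return to function is one. It simply does not supply the comparison for the listed scores.
- **That multiplicity is the defect.** Six scores at three visits plus two durations would make 6 × 3 + 2 = 20 contrasts, but the durations have to be constructed from the time points, and one contrast per instrument is an assumption. Naming one visit leaves 6 + 2 = 8, still without control. This supports naming a visit, but only weakly.

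**Conclusion.** The concern holds in this limited form: the synopsis commits to a comparison and defines no between-arm estimate for any secondary score or theatre time. The gap should be closed, but it does not touch the primary endpoint.

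The estimate that could be had from the same data has a 95% CI half-width of about 0.18 to 0.24 SD when adjusted for baseline, against 0.20 to 0.30 SD for the unadjusted change-score difference. These figures rest on 120 complete subjects per arm (240 is a maximum), equal SDs, and correlations of 0.3 to 0.7 that the documents do not give. Confidence is moderate, because only a synopsis is available. Adjustment does not remove unmeasured selection under rotated allocation, so the difference should not be read as a randomised effect.

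**What to change.** Add a short paragraph to Statistical Reporting, settled before any outcome data are seen:

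1. Report each secondary endpoint as a robotic-minus-conventional difference with a 95% CI.
2. For scores with a usable pre-operative value, adjust for the baseline score. Name one follow-up visit as the main one (1 year, for example) and treat the other two as supportive.
3. For theatre durations (patient in to out, incision to closure), which have no visit, and for any score without a usable baseline, report the difference between arms.
4. Keep the change-from-baseline tables, split by arm, as description. Give the unadjusted change-score difference as a sensitivity estimate.
5. Label the contrasts as estimates without multiplicity control, from rotated and non-randomised allocation.

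A repeated-measures model and adjustment for site are optional refinements.

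The cost is some wording and routine programming. No patients, visits or measurements are added, provided baseline scores are collected as the change endpoint implies. The drawback is that the adjusted and change-score estimates will disagree if the arms differ at baseline, which is why one must be declared the main estimate in advance.

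### Secondary scores are defined as raw change from baseline; baseline-adjusted follow-up values would compare the two groups at least as precisely, and Patient Satisfaction may have no baseline to subtract (minor)

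*Combined protocol and SAP*

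**What the plan says.** In the Study Synopsis, the Study Objectives/Endpoints row names comparison of the robotic and conventional techniques as the main purpose. The same row then sets a single definition for the clinical scores: "Evaluate the change of the following scores between baseline and each post-operative follow up for performance and clinical benefits". The list under it is "Oxford Knee Score • Objective Knee Assessment • Patient Satisfaction • EQ-5D • NRS Pain • FJS-12".

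The Scores/Performance Assessments row repeats that list under the words "Clinical performances are assessed by the following scores". Neither row identifies the satisfaction instrument, says what the item asks about, or states which scores are collected before surgery. The visit schedule is given once, for the study as a whole: "Follow-up visits at 6 weeks, 3 months and 1 year".

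Statistical Reporting plans descriptive summaries: "Continuous data, such as age, will be summarized by using means, medians, SD, minimum, maximum, and 95% CI over the time period of interest". It names no between-group model, baseline adjustment or test for the scores.

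**The concern.** One definition is applied to six instruments, and it raises two separate questions.

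The first is precision. Subtracting the baseline describes how a patient has progressed, but it is not the best use of the baseline when the question is whether two groups differ. Subtraction fixes the weight on the baseline at one whatever the correlation, and so can carry baseline noise into the group comparison. A regression covariate lets the data set the weight.

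The second is whether the endpoint can be computed. A change score needs the same question, with the same meaning, before and after surgery. For Patient Satisfaction the plan does not show that this holds. If the item asks about the operation or its result, no pre-operative answer can exist and the endpoint has no value. If it asks about the knee, a baseline is possible.

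At stake are wider intervals than necessary for the secondary scores, and one score whose definition might have to be settled after the data have been seen.

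**Working it through.** **Plan's own figure.** There is none to reproduce. The documents give no SD, correlation, effect size, alpha or power for any score.

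**Inputs from the documents.** The change rule and its six scores (Study Objectives/Endpoints); three post-operative visits (Length of Study); "Maximum study enrolment of 240 subjects in total, including 40 subjects in the CT sub cohort" (Sample Size); "Selection process should be rotated on an equal basis" (Study Design).

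**Assumed inputs.** k = baseline SD / follow-up SD, from 0.25 to 1; ρ = baseline-to-follow-up correlation, from 0 to 0.7. For power only: 240/2 = 120 per group (full enrolment, equal split), two-sided 0.05, and a true difference of 0.4 follow-up SD.

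**Formulas**, each relative to the variance of the follow-up value alone:

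- Change: 1 + k² − 2ρk
- Follow-up adjusted for baseline: 1 − ρ²
- Difference: (1 + k² − 2ρk) − (1 − ρ²) = k² − 2ρk + ρ² = (k − ρ)², which cannot be negative

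Change is noisier than the unadjusted follow-up value only when ρ < k/2. The CI ratio below is the square root of the change variance over the adjusted variance.

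| k | ρ | Change | Adjusted | CI ratio | Power, change | Power, adjusted |
|---|---|---|---|---|---|---|
| 1 | 0 | 2.00 | 1.00 | 1.41 | 59.1% | 87.3% |
| 1 | 0.2 | 1.60 | 0.96 | 1.29 | 68.8% | 88.5% |
| 1 | 0.5 | 1.00 | 0.75 | 1.15 | 87.3% | 94.7% |
| 1 | 0.7 | 0.60 | 0.51 | 1.08 | 97.9% | 99.1% |
| 0.5 | 0.5 | 0.75 | 0.75 | 1.00 | 94.7% | 94.7% |
| 0.25 | 0 | 1.06 | 1.00 | 1.03 | 85.2% | 87.3% |
| 0.25 | 0.2 | 0.96 | 0.96 | 1.00 | 88.5% | 88.5% |
| 0.25 | 0.5 | 0.81 | 0.75 | 1.04 | 93.0% | 94.7% |
| 0.25 | 0.7 | 0.71 | 0.51 | 1.18 | 95.6% | 99.1% |

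Power for the unadjusted follow-up value is 87.3% throughout. The two methods tie where k = ρ; everywhere else adjustment is more precise. When the baseline spread is small (k = 0.25), change is almost the follow-up value itself: at worst 6% more variance than follow-up alone (ρ = 0), and less once ρ exceeds 0.25/2 = 0.125.

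The formulas assume a common slope in the two groups and similar baseline distributions. They ignore the small cost of estimating the slope, which is negligible at this sample size.

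**Patient Satisfaction.** No arithmetic applies. The change rule presupposes a baseline value, yet nothing in the synopsis shows that the item has one with the same meaning as the post-operative value.

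**The case against.** The strongest reply is that little depends on this. The planned analysis is descriptive, no test or power is tied to the scores, and the primary endpoint (femoral rotation on CT) is unaffected. Computing change requires the post-operative values, so they could be reported anyway. That stands, and it is why the point is minor.

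Second, change is not always the noisier choice. With equal SDs it matches the unadjusted follow-up value at ρ = 0.5 and is more precise at ρ = 0.7. That also stands. The case for a covariate does not depend on change being worse than follow-up alone, only on its never being better than adjustment.

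Third, a change rule implies that a satisfaction baseline will be collected, and an item about the knee can be asked before surgery. This is fair. The text says only Patient Satisfaction, so a reader who infers satisfaction with the operation, and hence that every change value is undefined, goes further than the documents allow.

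A reader might also infer that FJS-12 sits near its worst value before knee replacement, so that subtracting it adds noise. The documents give no baseline level for FJS-12. The inference would not follow in any case, because a score bunched at its floor has little spread and then costs at most about 6% in variance at k = 0.25.

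Finally, allocation is by rotation and no randomisation is described. If the groups differ systematically at baseline, change and adjusted analyses can give different answers, and the precision argument alone does not decide between them. That is a reason to state the choice in advance and to show the baseline scores by group.

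**Conclusion.** The point holds as a low-cost improvement and not as a demonstrated error. For the robotic-versus-conventional comparison, the raw change score has a variance larger than the baseline-adjusted follow-up value by (k − ρ)², in units of the follow-up variance. Over the values tabulated, that ranges from nothing to a doubling, the doubling being at k = 1 and ρ = 0. Both k and ρ are assumptions, so the size for any particular score is unknown; only the direction is certain, given similar baselines and a common slope.

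For Patient Satisfaction the conclusion is conditional: change cannot be used if the item has no valid pre-operative value, and the documents do not settle whether it has one. Nor do they support a claim that satisfaction and FJS-12 separate the two techniques better than the other scores, or any reason to treat FJS-12 differently from another score that has a baseline. Severity is minor.

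**What to change.** In Study Objectives/Endpoints and Statistical Reporting:

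1. State for each score the instrument and whether it is collected before surgery.
2. Compare FJS-12 between groups at 6 weeks, 3 months and 1 year as the follow-up value with baseline as a covariate, giving the adjusted difference and its 95% CI. Apply the same to every other score with a valid baseline.
3. Keep within-group change from baseline as a descriptive summary for those scores, and tabulate baseline values by group.
4. For Patient Satisfaction, if the item has no valid pre-operative value, report the post-operative value by group at each of the three visits instead of change. The summaries already planned for continuous or categorical data are enough.

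The cost is a few lines of text and one simple regression per score and visit. No new data are needed, because the change rule already presupposes the baselines. Where satisfaction is reported at follow-up only, it loses the format shared with the other scores.

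### Robotic or conventional technique is assigned by a predictable, non-random rotation, with no stated concealment, by-arm baseline table or adjustment, so the main comparison is open to selection

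*Combined protocol and SAP*

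**What the plan says.** All references are to the Study Synopsis in the combined protocol and SAP.

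- **Allocation (Study Design).** "Selection process should be rotated on an equal basis. (eg. 5 Robotic TKA's followed by 5 Conventional TKA's", continuing until enrolment is complete. Five and five is an example; the rule itself is equal rotation.
- **Recruitment (Study Design).** "Each consecutive, potential and eligible patient presenting as a candidate for primary knee arthroplasty will be offered study participation".
- **Size (Sample Size).** "Maximum study enrolment of 240 subjects in total, including 40 subjects in the CT sub cohort".
- **Purpose (Study Objectives/Endpoints).** "The main purpose of this study is to collect and compare clinical outcomes data" under the two kinds of instrumentation. The primary endpoint is to "Evaluate the accuracy of implant alignment for ROSA total knee robotic instrumentation compared to conventional instrumentation", measured as femoral rotation on CT. The secondary endpoints are theatre time points and scores: "Evaluate the change of the following scores between baseline and each post-operative follow up for performance and clinical benefits".
- **Analysis (Statistical Reporting).** "Continuous data, such as age, will be summarized by using means, medians, SD, minimum, maximum, and 95% CI over the time period of interest", with counts and percentages for data such as gender. For CT: "The data from the CT sub cohort will detect for a difference in deviation from the initial alignment target proportions".

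The supplied text mentions neither random assignment nor concealment, and does not say whether technique is fixed before or after consent. Statistical Reporting does not say that baseline summaries are split by arm, and it names no covariate.

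**The concern.** Under a rotation known to the site, the technique for the next patient is known before that patient is approached, judged eligible, consented or booked. A knee expected to be difficult can be held for a later run, or a patient can decline once the technique is clear. The arms may then differ in case mix, and part of any observed difference would come from who was operated on in which run.

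This matters because the between-technique comparison is the reason for the study. A non-randomised comparison relies on showing the arms' baseline characteristics side by side and adjusting for them. The plan collects much of what is needed but specifies neither step, so sorting between runs would be neither visible nor corrected in the specified output.

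**Working it through.** The plan gives no figure to reproduce here: no alpha, power, effect size or SD is stated. The check has three parts.

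**1. How predictable is the next assignment?**

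- Known 5+5 rotation: 100%.
- Permuted block of 10, block size known and all past assignments visible, guessing the arm with more places left (b = 5 per arm): [b + (2^(2b)/C(2b,b) - 1)/2]/(2b) = [5 + (1024/252 - 1)/2]/10 = 65.3%.
- Blocks of varying size, simulated over 20,000 lists of 30: 68.8% (sizes 4/6) and 64.3% (sizes 8/10/12).
- Fully concealed list: 50%.

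**2. How large could the bias be?**

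From the documents: 240 subjects on an equal basis gives 240/2 = 120 per arm, and 40 CT subjects gives 40/2 = 20 per arm if split equally (the split is assumed).

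Assumed, with no source in the documents:
- share of difficult knees f = 0.2 or 0.3;
- their outcome worse by D = 0.5 or 1.0 SD (SD within difficult or within ordinary knees);
- fraction s of difficult knees arriving in a robotic run and deferred to the next conventional run, from 0 to 0.5, always in that direction;
- a continuous outcome with a simple 95% interval for the arm difference. The plan specifies no such interval for scores or times and words the CT comparison in terms of proportions.

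Formulas:
- difficult share, robotic: pr = f(1 - s)/(1 - fs); conventional: pc = 2f - pr
- spurious shift = (pc - pr) × D
- SE = sqrt{(2 + D²[pr(1 - pr) + pc(1 - pc)])/n}
- miss rate = P(Z > 1.96 - shift/SE) + P(Z < -1.96 - shift/SE)

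Worst case shown (f = 0.3, s = 0.5, D = 1): pr = 0.15/0.85 = 17.6%, pc = 60% - 17.6% = 42.4%, shift = 0.247 SD. At n = 120, SE = sqrt(2.3895/120) = 0.141 and the miss rate is 41.7%. At n = 20, SE = 0.346 and the miss rate is 11.0%.

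| Deferred (s) | Shift, SD | Miss rate, 120 per arm | Miss rate, 20 per arm |
|---|---|---|---|
| 0 | 0 | 5.0% | 5.0% |
| 5-10% | 0.008-0.043 | 5.0-6.1% | 5.0-5.2% |
| 25-50% | 0.042-0.247 | 6.2-41.7% | 5.2-11.0% |

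Each range covers all combinations of f and D. If SD is read as the total within-arm SD, the upper ends in the last row become 48.2% and 12.2%.

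**3. How much would adjustment recover?**

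For a baseline covariate that separates difficult from ordinary knees by k SD, the share of the shift left is 1/(1 + k²v), where v is the mean of p(1 - p) over the two arms. At 25-50% deferral, k = 1 leaves 83-87% and k = 2 leaves 55-62%. Adjustment helps but does not replace unpredictable assignment.

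**The case against.** The strongest reply has five parts.

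- **The study does not claim randomisation.** This stands. The point is a design weakness, not a contradiction in the documents.
- **Consecutive patients are offered participation and short runs keep the arms close in time.** Both help. The first limits who is approached and the second limits calendar drift. Neither stops deferral or refusal once the technique is foreseen, although heavy deferral would itself depart from the rotation as written.
- **No document supplies a deferral rate, a difficult share or a direction.** This stands. Sorting in opposite directions could cancel, and light deferral is almost harmless, which is why the range starts at zero. No value within it is an estimate.
- **Scores are taken as change from baseline, and by-group reporting is a plausible reading of a study divided into two groups.** Change scores do not cover theatre times or case-mix differences in improvement. By-group baseline reporting is plausible but not stated.
- **The source is a synopsis, and consent pages are not in the text reviewed.** This stands. The rotation is certain; the missing safeguards are missing only from the supplied text.

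A reader might infer that the rotation undermines the CT primary endpoint. The documents do not support that: at 20 per arm sampling noise dominates, and nothing shows that harder knees deviate more from their own alignment target. A reader might also attribute learning effects with the robot to this rule, but those would remain under any allocation.

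**Conclusion.** The concern holds as a design weakness that should be fixed. Technique is assigned by a foreseeable, non-random rule, and the supplied text specifies no concealment, no by-arm baseline comparison and no adjustment for the comparison that is the study's purpose. The comparison is open to selection. It does not follow, as a reader might infer, that selection will happen or that the results will be invalid.

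The practical exposure is mainly in the full-cohort comparisons of scores and theatre times. There it ranges from nothing to a serious inflation, depending wholly on an assumed amount of one-way deferral. The exposure of the primary endpoint is small. Those error rates describe an interval that a reader of a comparative study would naturally form, not one the plan sets out for scores or times.

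**What to change.** Replace the rotation sentence in Study Design with:

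> Subjects are assigned 1:1 within site from a computer-generated list (permuted blocks of randomly varying size), held in the EDC and released only after consent and baseline scores are entered. CT sub cohort membership is recorded before assignment. Analysis is by assigned group.

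In either design, add to Statistical Reporting:

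> Baseline characteristics and scores are tabulated by arm. Score comparisons are adjusted for the baseline score (where collected), age and site; theatre times are adjusted for site.

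If theatre logistics require runs of five, also adjust theatre times for case number, describe the comparison as non-randomised, and state that adjustment removes only part of any selection bias. Randomising which technique opens each pair of runs would not be an adequate substitute: once the first case in a pair is known, the other nine of ten are certain.

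**Cost.** The list needs protocol and consent wording with ethics review, plus set-up in the web database already planned. Robot and theatre scheduling becomes less predictable; any effect on refusals cannot be judged from the documents. Equal allocation is already directed, so patient numbers and procedures do not change. The tables and adjustment need only analysis text and use data already collected.
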